48. Added information about storing fMRI data under unique numeric identifier and acrostic, but adding year of birth, in case a radiologist has to assess the brain scan (D.1.a.) (8/16/2016).
49. Added links to Martinos security and imaging manuals for reference (D.1., D.2.d.2) (8/16/2016).

Version 1.4:

Version Date: (February 8th, 2017)

1. Added post-treatment study visits 2 (12 weeks after baseline) and 3 (16 weeks after baseline). For each of these additional visits, patient participants will fill out the Action Plan Initiation Survey (APIS-5). Compensation is \$5 for each of these study visits, which will be dispersed at the final 6-month follow-up visit for a total of \$30 as the final payment (C.3.d.3.) (10/31/16).
2. Modified APIS-5 and APA-10 instruments to include 6 categories of action plan goals for patient participants to choose from (activity level/exercise, diet/eating/drinking, sleep, self-care practice, medication, and reducing substance use) (C.3.f.6.) (10/31/16).
3. Adapted orientation and informed consent procedure, so that information sheet instead of informed consent are distributed at the orientation session (C.2.c, C.3.d.3, D.2.d.2.3, D.5.c) (11/7/16).
4. Elimination of two survey sessions (10-12 week and 56-week) survey sessions for PCPs who enroll in the study from this point onwards. We are naming this PCP group "Group 3" to distinguish from existing PCP Groups 1 and 2 (11/7/16).

5. Addition of 2 questions regarding actual pain level during the scan and 18 questions, immediately after scanning, regarding the subjective experience with the tasks during the scans (fmri questions) (C.3.f.14.) (11/7/16).
6. Changed instance of first contact about the optional fMRI pilot study from the MINDFUL-PC orientation session to a phone call prior to the MINDFUL-PC orientation session, with the option of sending the fMRI pilot study flyer and information sheet about the optional fMRI pilot study via email prior to the MINDFUL-PC orientation session.

Version 1.5:

Version Date: (April 6, 2017)

1. PCP Enrollment has been completed as of February 10th, 2017
2. Remove PCP Visit Study Session for Patient Participants
3. Expand referral requirements: patients can be referred to MINDFUL-PC by either a licensed CHA primary care provider, or a licensed CHA mental health clinician.
4. Add Action Plan Study Session for Patients during Study Weeks 6-7

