5. Add Action Plan Worksheet as a study material to be completed by patients during Action Plan Study Session
6. Modify APIS-5 Survey to reflect changes in Action Plan Worksheet
7. Change APIS-5 study sessions to Weeks 9,10, and 16 (\$5 compensation each)
8. Add Study Completion Bonus of \$30 to be disbursed at end of study if all study participation items have been completed (Total compensation is now \$140).
9. Study payments occur three times: at baseline (up to \$20), at 8 weeks (up to \$40), and at 24 weeks (up to \$80).
10. Clarified which/how many surveys waitlist participants need to complete in order to be eligible for a spot in the next MTPC group once their 6-month study participation is over
11. Clarified how surveys completed on paper will be handled
12. Add two research assistants: [name] and [name]

Version 1.6:

Version Date: (April 25, 2017)

1. Add one research assistant: [name]

Version 1.7: Version Date: (May 24, 2017)

1. Add one research assistant ([name])

Version 1.8: Version Date: (Add date of approval of Amendment 23)

1. Add one research coordinator ([name])

Version 1.9: Version Date: (June 13, 2017)

1. Add one research assistant ([name])

Version 1.10: Version Date: (July 25, 2017)

1. Add two research assistants ([name] and [name])

2. Add patient participant adverse events self-report form to be completed at the 8-week and 6-month study sessions
3. Add “STOP ACHE GO” to the patient participant mindfulness practice diary. STOP ACHE GO stands for:
 Stop or Slow down
 Turn towards experience or Take notice of breathing
 Observe with Openness
 Pleasantness/UnPleasantness
 Allow it to be as it is/Accept the ACHE is here/Anchoring to present with breathing
 Compassion/Curiosity
 Holding the experience with warmth
 Expand awareness from ACHE to breathing, then to body, then to all the senses
 Gratitude/Grounding in values
 Open to life, its challenges and beauty/Orient towards experience with kindness

Version 1.11: Version Date: (Retracted on September 26, 2017)

1. Add one research assistant ([name])

Version 1.12: Version Date: (October 2, 2017)

1. Add Health, Eating, Activity, and Rest Tracking (HEART) pilot study informed consent and procedures for alumni cohort and concurrent cohort
2. Remove scales HCCQ, VAS, PDRQ, and action plan interview
3. Add compensation related to HEART pilot study

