Any patient participant who is eligible with a screen, has completed the informed consent form at the orientation session, and has completed the baseline assessment battery will be eligible for placement on our program list and ultimately randomization into either of the two groups using a stratification algorithm. Randomized patients will be stratified with two layers based on PCP group and health center location. PCPs who refer after the PCP portion of the study closes will be considered “non-trained” (equivalent to Groups 2 and 3) for purposes of randomization. We will begin with 4 health center regions (Malden, Revere, Somerville, and Cambridge) and health centers within each region will have their own list, but ultimately hope to expand so that each participating health center location with a mindfulness-trained behaviorist will have its own waitlist for new groups. When a new group is scheduled to open at a health center location, those patients with PCPs at that health center location will be randomized to either intervention group or control (First stratification layer—Location). Patients with a PCP from another health center but who have a specific language need may be included on the waitlist for capability of that health center. We hypothesize an increased rate of MTPC patient referrals from PCPs who are enrolled in the mindfulness training program versus those who only received information about mindfulness-based interventions. Therefore, within each group location, in order to achieve an optimal 2 x 2 factorial structure (see randomization schema figure), patients will be randomized using a second stratification layer based on the primary care provider’s level of mindfulness training (Group 1 vs. Group 2 or Group 3) to either 8-week MTPC or one 60-min introduction to mindfulness, using a 2:1 randomization ratio, respectively (Second stratification layer—PCP Group), based on the second layer of stratification (See Table 1). Study staff will maintain the waitlists and then notify the patient participants of their acceptance into either group.

Table 1. Randomization Schema:

	MTPC Group	Control Group
Group 1: Providers with Mindfulness Training	145	72
Group 2 and 3: Providers with introduction & community referral	145	72

2 x 2 Factorial design testing main effects of patient training and primary care provider training, as well as the interaction of the combination.

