PCP Training		Phase 1a: MBSR training		Phase 1b:	Phase 2: Mindful Communication		
Primary care providers	Medicine Grand Rounds	8 MBSR sessions (2.5 hours each) for Group 1a	MBSR all-day retreat	Weekend retreat for Group 1b	Monthly meetings for 10 months (2.5 hours each)		
Group Leader Training		Phase 1: MBSR with PCPs			Phase 2: Group Leader training		Phase 3: Supervision
Behavioral health clinicians	Psychiatry Grand Rounds	8 MBSR sessions + practicum (3.5 hrs each)	MBSR all-day retreat		Weekend Retreat 1 (16 hrs) Jan 2015	Weekend Retreat 2 (16 hrs) Feb 2015	Weekly Group MTPC Group Leader Supervision (9 months, 1.5 hrs/week)
Timeline:	10/1/2014	10/22/2014 - 12/17/2014		1/9/2015- 1/11/2015	1/16/2015 - 12/16/2015		

C.4.b. Current Implementation Staging Map:

Each primary care region will be assigned a hub based on space and staffing considerations. During training, primary care provider champions and behavioral care leaders will be identified within each regional primary care region to support recruitment and implementation at sites in their region. This program aims to begin patient enrollment in September 2015 at 2 regional hub primary care centers with groups starting around October 2015. After this first round of groups are completed, we will review the process to evaluate for improvements prior to a second round of groups. Additional health center group space will likely become available in late 2015 to add two additional centers as group sites, as well as the potential use of CHA hospital group rooms to provide MTPC groups, bringing the total to 6 PCMHs with on-site groups. We will begin recruitment for groups that meet the needs of cultural and linguistically diverse communities with several different groups for LEP patients starting in late 2016. We plan to offer MTPC groups in Spanish and Portuguese by early Fall 2016. Planning for a third implementation step will await development of space and a further roll-out in integration of mental health into the patient-centered medical homes in order to expand to the full set of sites.

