Mixed Effects Modeling to evaluate for main effects of PCP mindfulness training and main effects of Patient training level (1 hour vs. 8 week) for each survey, as well as the interaction effect with relevant covariates.

3. *Health Outcomes Hypotheses*: We hypothesize reductions in depression, anxiety and stress as a main effect of MTPC. Finally, we hypothesize reductions in use of medications prescribed for symptom reduction (benzodiazepines, opioids, etc.), overall improvement in markers of health maintenance and chronic illness management (i.e. PQRS data). We hypothesize the highest levels of initiation and maintenance of self-management action plans among MTPC group with Mindfulness-trained providers.

Mixed Effects Modeling to evaluate for main effects of PCP mindfulness training, main effects of Patient training level (1 hour vs. 8 week) for each outcome, as well as the interaction effect with relevant covariates.

4. *Provider Resilience Hypothesis*: We hypothesize greater workplace well-being, reduced experience of burnout, and increased resiliency among providers as a main effect of provider MBSR + Mindful Communication training.

We will use Mixed Effects Modeling to evaluate for main effects of PCP mindfulness training and time for each survey and the interaction of the two.

5. *Medical Regimen Adherence Hypotheses*: We hypothesize a main effect of MTPC group status on levels of initiation and maintenance of medical regimen health behavior change, as measured by the APIS-5 self-report score. The highest levels will be demonstrated among the MTPC group participants with mindfulness-trained providers. We hypothesize that total formal mindfulness practice, post-study total mindfulness score, baseline mindful non-judgment score, and self-compassion will be associated with successful initiation and maintenance of action plans. Action plan initiation will be validated by increases in step count, and increases in number of active periods, changes in sleep, changes in mindfulness practice, and changes in nutritional habits.

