Using an intent-to-treat analysis, we will use logistic regression and Mixed Effects Modeling to evaluate for main effects of MTPC, mindfulness-trained PCPS, and the interaction of the two on binary and continuous ratings of level of action plan initiation and maintenance. We will conduct exploratory linear regression models of post-study mindfulness and self-compassion and overall practice dose as independent variables with level of action plan initiation and maintenance as dependent variables.

The experimental fMRI pilot analyses methods are described below.

6. *Self-Regulation Mechanisms Hypotheses*: In 4 different fMRI tasks, we hypothesize (a) greater activation of ACC and OFC and decreased activation in the amygdala/hippocampus after MTPC intervention compared to before intervention (i.e. a pre/post increase) in an emotional Go/NoGo inhibitory control task, as in Perez 2016 [69], using validated emotional pictures (International Affective Pictures System, IAPS, [70]). The task includes 448 IAPS pictures (50% neutral and 50% unpleasant), which will

be presented briefly (1.5 seconds), while participants either react (Go) or withhold a button press reaction (NoGo), depending on abstract symbols presented on top of the pictures; (b) greater activation of mid-posterior insula after (compared to before) MTPC in a self-compassion task (that contrasts a self-reassurance condition with a self-criticism condition), as in Longe 2010 [71]; (c) greater insula activation during an interoceptive attention task (that contrasts an interoceptive attention condition with an exteroceptive attention condition) as in Farb 2013[72], and d) increases in the rostral ACC (rACC) and ventromedial prefrontal cortex (vmPFC) during the **anticipation of pain** after compared to before MTPC and increased activation in the lateral prefrontal cortex (LPFC) and somatosensory areas **during pain** after compared to before the MTPC, as in Kim 2013 [73]. We hypothesize that all inhibitory control and interoceptive targets will be associated with higher levels of initiation of regimen adherence, while self-compassion, emotion/pain regulation, and interoceptive targets will be associated with higher levels of regimen maintenance.

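### The hypothesis 5 model pools action plan outcomes from before and after the April 2017 procedure change with no version term, which leaves the non-randomised PCP-training effect exposed

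*Combined protocol and SAP*

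**What the plan says.** Hypothesis 5 in C.5.b takes initiation and maintenance of the action plan "as measured by the APIS-5 self-report score". The analysis is by intention to treat, with logistic and mixed models "to evaluate for main effects of MTPC, mindfulness-trained PCPS, and the interaction of the two". The entries for hypotheses 2 and 3 add "as well as the interaction effect with relevant covariates"; hypothesis 5 does not say even that. C.3.c stratifies randomisation by PCP group and health center location, not by calendar period.

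The change log for version 1.5, dated April 6, 2017, lists "Remove PCP Visit Study Session for Patient Participants", a new Action Plan session in weeks 6-7 with a worksheet, "Modify APIS-5 Survey to reflect changes in Action Plan Worksheet", and a move of the APIS-5 sessions to weeks 9, 10 and 16. I use the log only as evidence that data collection changed during the trial, not as a conflict of text. The earlier procedure is also still visible in current sections: C.3.f.6 describes APIS-5 goals as made with the PCP, and C.3.f.11 and D.10.a describe plans made at the PCP visit.

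On timing, C.4.b states "This program aims to begin patient enrollment in September 2015". PCP recruitment closed on February 10, 2017 (C.2.a).

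On PCP status, C.3.a says providers sort themselves into training or no training, and that Group 3, enrolled after October 2016, gets no training. C.3.c adds that "PCPs who refer after the PCP portion of the study closes will be considered" untrained for randomisation.

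**The concern.** A plan agreed with a provider at a visit and a plan written alone on a worksheet need not be initiated at the same rate. Nor need two forms of the survey, given at different weeks, record the same rate. If the old and new procedures differ, and if patients of trained PCPs fall mostly under the old one, a model without a version term attributes part of the procedural difference to PCP training. Randomisation gives no protection here, because PCP training was not assigned at random. At stake are the PCP main effect for this outcome and, secondarily, the meaning of an MTPC effect that is an unlabelled average over two procedures.

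**Working it through.** **The plan's own figure.** C.5.c gives 80% power for 0.68 (n = 290) versus 0.54 (n = 144), two-sided 0.05. The pooled rate is (144 x 0.54 + 290 x 0.68)/434 = 0.634. The null SE is 0.0491 and the alternative SE 0.0498. Power = Φ[(0.14 - 1.96 x 0.0491)/0.0498] = 81.0% (80.3% unpooled). The figure reproduces and is not in dispute.

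**Does untrained status lean late?** Three facts say it probably does: Group 3 is wholly untrained and enrolled after October 2016; PCP enrolment closed about eight weeks before version 1.5; and PCPs who refer after closure are coded untrained. The lean is partial. Group 2 is untrained but early, and I read the post-closure rule as covering PCPs not already enrolled, so that Group 1 PCPs can still supply late patients to the trained row.

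**PCP main effect.** Let e_T and e_U be the shares of trained-row and untrained-row patients under the old procedure, and s the shift in initiation rate between procedures. With no true PCP effect:

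false PCP difference d = (e_T - e_U) x s.

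Table 1 gives 145 + 72 = 217 patients per PCP row. The average planned rate at 2:1 is (2 x 0.68 + 0.54)/3 = 0.633. With rates 0.633 ± d/2, the SE is about 0.046, and the rejection rate is 1 - Φ(1.96 - d/SE) + Φ(-1.96 - d/SE). The documents give neither the shares nor the shift, so both are assumptions.

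| e_T - e_U | s | d | rejection rate |
|---|---|---|---|
| 0 | any | 0 | 5.0% |
| 0.20 | 0.05 | 0.01 | 5.5% |
| 0.30 | 0.10 | 0.03 | 9.9% |
| 0.30 | 0.20 | 0.06 | 25.5% |
| 0.50 | 0.20 | 0.10 | 58.5% |

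The last row is 60.1% if computed as 0.62 versus 0.72.

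**MTPC effect and interaction.** Within a PCP row, both arms are randomised as each group opens, so they share the same early share e. Under an additive shift, MTPC minus control is δ + (e - e) x s = δ in each row. The shift cancels from the MTPC effect and from the difference between rows, exactly on the risk-difference scale and approximately on the logit scale. If the MTPC effect is δ_1 under the old procedure and δ_2 under the new, the interaction picks up (e_T - e_U) x (δ_1 - δ_2). For example, 0.30 x 0.10 = 0.03.

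**Does a version term repair it?** Logistic models were simulated with 1,500 runs per scenario, 434 patients, no true PCP effect, and early shares of 70% and 30%. The PCP false-positive rate without and with a version term was 14.5% and 5.6% for a shift of 0.10, 24.0% and 6.1% for 0.14, and 41.3% and 4.8% for 0.20. Power for MTPC stayed at about 80-82% with or without the term.

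**The case against.** The strongest reply is that the trial was sized on MTPC versus orientation only, and that contrast is randomised. Hypothesis 5 predicts an MTPC main effect and the highest levels in the doubly trained cell; the PCP main effect enters only as a model term. The design is openly quasi-experimental for PCPs, and self-selection into training is a larger threat than version. All of this stands, and it limits the weight of the point. It does not explain why a known, dated change in the outcome should be left out of a model that still reports a PCP effect.

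Other parts of the reply also stand:

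- A reader might infer that the interaction is confounded outright. It is not, because an additive shift largely cancels.
- A reader might infer that opening referral to mental-health clinicians in version 1.5 made late patients untrained. The stratum follows the training of the patient's own PCP (C.3.a, C.3.c), and every patient must have one, so the referral route does not set it.
- If the removed visit was how a trained PCP shaped the plan, an early PCP effect would be real effect modification, not an artefact. A version x PCP group term is needed to see it.
- Two procedures is a simplification. Version 1.4 (February 2017) had already changed the APIS-5 goal categories and added APIS-5 visits, and some patients straddle the version 1.5 change.
- A 20-point shift exceeds the 14-point treatment effect the trial assumes, so the upper rates are extremes.

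Hypothesis 3 also covers action plans and allows covariates, but it names none, so it does not close the gap.

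**Conclusion.** The point holds for the PCP-training main effect: as specified, that estimate can absorb a shift between action plan versions. The MTPC main effect is largely protected and needs only to be reported as an average over procedures. The interaction is at risk only if the MTPC effect itself changed with the procedure.

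A reader might go further and conclude that a bias exists, or that it favours trained PCPs. The documents do not support either. They give no counts of patients by date and PCP group and no estimate of the version shift. September 2015 is a planned start, and nothing states how many patients made plans under the old procedure. The range of 1 to 10 points, with rejection from about 5.5% to about 60%, rests wholly on the assumed shares and shifts. Its low end is harmless. The change is worth making because it is cheap and shows whether the problem is present.

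**What to change.** In C.5.b, hypothesis 5, add action plan version as a fixed factor in the logistic and mixed models, defined by whether the patient's week 6-7 session fell before or after version 1.5 took effect. Also specify:

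- a table of randomised patients by version and PCP group;
- the MTPC effect reported by version;
- version x PCP group as a sensitivity analysis;
- a further sensitivity analysis that separates or excludes patients who straddle the change or fall under version 1.4.

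The factor can be assigned from dates the study already holds. To make that assignment clear, reconcile the current descriptions: C.3.f.6 gives APIS-5 weeks 8, 12 and 16 against 9, 10 and 16 in C.3.d.2, and six goal categories for the APIS-5 against three for the worksheet.

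The cost is one or two degrees of freedom and a somewhat less precise PCP estimate. MTPC power is about unchanged. Self-selection of PCPs into training remains a limitation and should be stated beside the result.

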The **Perceived Control Questionnaire (PCQ)** is adapted from a 5-item perceived control measure from Jerant et al. [55] and a previously validated survey from Armitage et al. [56]. This 5-item scale ask participants to rate their sense of control over chronic illness self-management on a 7-point scale from 1 (*None*) to 7 (*Total*). Items include "How much personal control do you have over your self-management behaviors?" Duration: 3 min.

Action Plan Worksheet/SMART Goal Video: Patient participants will complete the Action Plan Worksheet and watch a brief video about creating SMART goals (for example, <https://www.youtube.com/watch?v=1-SvuFIQjK8>) in PT Study Week 7. The Action Plan Worksheet is a 13-item worksheet that incorporates information about SMART goals to support patient participants to make a goal about their health in one of 3 categories (activity level/exercise, diet/eating/drinking, or mindfulness meditation practice). Patients are encouraged to share this worksheet with a person who may help the patient in accomplishing the goal, and/or a healthcare provider. Duration: 15 min.

Patients will complete the self-report **Action Plan Assessment (APA-10)** questionnaire after filling out the Action Plan Worksheet, at PT Study Week 7. This survey instrument is developed as an adaptation of two self-determination theory scales [57] [58] and incorporates elements of shared decision-making [59] and self-efficacy and barrier appraisal [60]. This 10-item scale evaluates patient behavior in the domains of self-determination, motivation, shared decision-making, and barrier appraisal. Participants are asked to rate their agreement with a statement on

a 7-point scale from 1 (*Strongly Disagree*) to 7 (*Strongly Agree*). A sample item includes “I have agreed to this action plan because I want to do it for myself.” Duration: 5 minutes.

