Patient participants in the MTPC Group and in the Waitlist Group will complete the mindfulness practice diary card every week for patient study weeks 1-8, throughout their MTPC training. Both groups of patient participants will complete this card for the week preceding the post-treatment survey session and the week preceding the follow-up survey session. Participants in the **concurrent cohort** of the HEART pilot study will also complete this survey for 1 week prior to MTPC Session 1 and for four weeks during MINDFUL-PC study weeks 5 and 9.

C.3.f.10. Mindfulness Resources Use Survey:

The **Mindfulness Resources Use Survey** is a 7-item weekly survey that asks about the frequency of use of community or mobile mindfulness resources as listed on the Community Resources handout given to all patients during the orientation session. This survey asks patients whether they have visited local mindfulness or meditation centers in person, whether they have used mindfulness guided recordings or apps online, and whether they have read any mindfulness-related books. It also asked about some related activities where people often practice mindfulness such as yoga, spiritual activities, and places of worship. A patient's total mindfulness resource utilization will be calculated by study personnel weekly. This survey will be completed by every study participant for Study weeks 1-8, and during the Follow-Up Survey Session at patient study week 36. Participants in the MTPC group will fill out the resources diary on a scantron sheet, and participants in the control group will fill out the resources diary on an online REDCap form. Participants in the **concurrent cohort** of the HEART pilot study will also complete this survey for 1 week prior to MTPC Session 1 and for four weeks during MINDFUL-PC study weeks 5 through 9. Duration: 5 min.

C.3.f.11. Reports from Electronic Medical Records for Patient Participants:

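### The exploratory regressions for action plan initiation name no arm term and no single-arm restriction, so the treatment effect can pass for a practice or mindfulness association; baseline non-judgment, a hypothesised predictor, has no planned analysis

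*Combined protocol and SAP*

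**What the plan says.** Hypothesis 5 (Medical Regimen Adherence, A.2.b and C.5.b) has two parts. The first concerns treatment: "We hypothesize a main effect of MTPC group status on levels of initiation and maintenance of medical regimen health behavior change". The second concerns predictors. Besides the total amount of formal practice, it names these: "post-study total mindfulness score, baseline mindful non-judgment score, and self-compassion will be associated with successful initiation and maintenance of action plans".

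The analysis paragraph in C.5.b treats the two parts differently. For treatment it plans intent-to-treat logistic and mixed models, whose targets are given as "main effects of MTPC, mindfulness-trained PCPS, and the interaction of the two on binary and continuous ratings of level of action plan initiation"; the same models cover maintenance. For the predictors it gives one sentence, which opens: "We will conduct exploratory linear regression models of post-study mindfulness and self-compassion and overall practice dose as independent variables". The outcomes it names are how far action plans were initiated and maintained. That sentence does not mention arm, PCP group, other covariates or the analysis population. It does not list baseline non-judgment.

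The predictors exist in both arms. Section C.3.f.9 says: "Patient participants in the MTPC Group and in the Waitlist Group will complete the mindfulness practice diary card every week". The week 8 battery, which includes the FFMQ and SCS-SF, goes to both groups (C.3.d.2; Appendix A, Table 3). Both scales are also completed before treatment, and the FFMQ has a non-judging facet (C.3.f.3).

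The Action Plan Worksheet (C.3.f.6) allows a goal in one of three categories: "activity level/exercise, diet/eating/drinking, or mindfulness meditation practice".

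**The concern.** MTPC teaches mindfulness and asks for daily home practice, so practice dose and post-study mindfulness should be higher in that arm. The trial also expects more initiation there. When arm moves both a predictor and an outcome, the two correlate across the pooled sample even if, within each arm, patients who practise more do no better than those who practise less. A pooled coefficient without arm then partly restates the randomised result as a practice or mindfulness association.

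This matters because no other planned analysis addresses the predictor part of hypothesis 5, and section B presents the study as a way to test targets that may explain how mindfulness affects adherence. An association carried only by the arm difference says nothing about that.

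The missing baseline predictor is a separate matter: a stated hypothesis with data but no model.

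**Working it through.** **Inputs from the documents (C.5.c, repeated in D.4.c).** 290 MTPC and 144 control patients (434 in total); initiation 0.68 and 0.54; two-sided 0.05; stated power 80%.

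**Assumption.** The arm difference d in the predictor, in within-arm SD units. The documents give no figure, so a range of 0 to 2 is shown.

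**Step 1: reproduce the plan's figure.** Pooled rate p = (144 × 0.54 + 290 × 0.68)/434 = 274.96/434 = 0.6336.
- SE under the null = √[0.6336 × 0.3664 × (1/144 + 1/290)] = 0.0491.
- SE under the alternative = √[0.54 × 0.46/144 + 0.68 × 0.32/290] = 0.0498.
- Power = Φ[(0.14 − 1.96 × 0.0491)/0.0498] = Φ(0.88) = 81%, which agrees with the stated 80%.

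**Step 2: correlation of arm with initiation.** With q = 290/434 = 0.668, √[q(1 − q)] = 0.471. Then φ = 0.14 × 0.471/√(0.6336 × 0.3664) = 0.137.

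**Step 3: correlation induced by arm alone.** The correlation of arm with the predictor is r_A = d × 0.471/√(1 + d² × 0.2217). With no association inside either arm, the pooled correlation of predictor with initiation is r_A × φ.
- d = 0.5: 0.229 × 0.137 = 0.031
- d = 1: 0.426 × 0.137 = 0.058
- d = 2: 0.686 × 0.137 = 0.094

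**Step 4: rejection rate at nominal 5%.** 4,000 simulated trials per row, linear regression of initiation on one predictor, no within-arm association.

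| d (SD, assumed) | No arm term, 0.68 vs 0.54 | Arm included, 0.68 vs 0.54 | No arm term, 0.54 in both arms |
|---|---|---|---|
| 0 | 4.8% | 4.9% | 4.9% |
| 0.2 | 5.7% | 5.1% | 5.2% |
| 0.5 | 10.1% | 5.3% | 5.3% |
| 0.8 | 16.2% | 4.9% | 4.8% |
| 1.0 | 21.9% | 4.7% | 5.4% |
| 1.5 | 38.1% | 4.8% | 4.9% |
| 2.0 | 50.0% | 5.1% | 5.7% |

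A normal approximation with mean r√434 gives the same picture. For d = 1, 0.058 × 20.8 = 1.21, and the chance of exceeding 1.96 in absolute value is about 23%. For d = 0.5 and d = 2 it gives about 10% and 50%.

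**Step 5: baseline non-judgment.** The predictors hypothesised are total formal practice, post-study mindfulness, baseline non-judgment and self-compassion. Those in the model sentence are practice dose, post-study mindfulness and self-compassion. Baseline non-judgment is the one left out. It is measured before randomisation and so is independent of arm in expectation, which means its omission plays no part in the inflation above.

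**The case against.** Several points on the other side are fair.

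- **Pooling is not stated.** A reader might infer that the plan commits to pooling the arms without adjustment. It does not; it is silent. Pooling is still the natural reading, because the data come from both arms, the preceding sentence names MTPC when it is wanted, and hypotheses 2 and 3 mention covariates explicitly.
- **A spurious result is not assured.** The induced correlations are small (0.03 to 0.09 for d from 0.5 to 2). Rejection reaches one half only at an assumed 2 SD, and there is no inflation if MTPC does not change initiation. Nor is randomisation the cause: MTPC must affect both predictor and outcome.
- **The hypothesis speaks only of association.** A pooled association would be real in the trial population and could include mediation, so these rejections are false only for a within-arm relation. That stands. But when the association comes entirely from the arm difference, it adds nothing to the randomised comparison, and separating a mediator's link with outcome from the treatment effect itself calls for arm in the model.
- **The simulation is simpler than the plan.** It tests one predictor against a binary outcome. The planned outcome is a level, and the sentence can be read as a joint model. The percentages are illustrative; a joint model would change them but not the direction.
- **Linear models.** A reader might infer that these are wrong because initiation is binary. The plan recognises binary and continuous ratings, and the HEART analysis in C.5.b applies a cut-off of 5 or more to the APIS-5, which implies a graded score. A linear model is defensible for that.
- **Dose and outcome as one behaviour.** A reader might infer this for patients whose goal is mindfulness practice. Most weekly diaries (weeks 1-8) precede the goal set in weeks 6-7, initiation is surveyed from week 8 onwards, and the documents give no share of patients choosing that goal. This supports a sensitivity check, no more.

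**Conclusion.** The point holds as a gap in specification with a real consequence. If the models are run with only the listed predictors on both arms, and MTPC raises both predictor and initiation, a nominal 5% test rejects in about 10%, 22% and 50% of trials at assumed shifts of 0.5, 1 and 2 SD, against about 5% with arm included. This rests on the plan's own initiation rates and arm sizes, on no within-arm association, and on shifts that the documents do not supply. The absence of any analysis of baseline non-judgment is a second, independent gap. Severity is minor: the models are labelled exploratory, and neither the intent-to-treat comparison nor its sample size is affected.

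**What to change.** In C.5.b, hypothesis 5:
- State which arms the exploratory models include.
- Add arm to every model and, for post-study mindfulness and self-compassion, the baseline value of that score. For practice dose, fitting within MTPC is an alternative.
- Add baseline non-judgment as a predictor of initiation and maintenance.
- Optionally, repeat the dose model without patients whose action plan goal is mindfulness practice.
- Report the results as exploratory. Adjusted and within-arm associations remain observational and can still be confounded, for example by motivation, so an arm term alone does not establish a dose effect or a mechanism.

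The cost is a few sentences and model terms. All the data are already in the assessment schedule.
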